Gait Modification Treatments for Knee Pathology
NCT: 03116230
September 7, 2017

Study Protocol and Statistical Analysis Plan

Project Title. Analysis of Pain, Function, and Joint Mechanics in Response to Two Treatments for Knee Pathology

Purpose. The objective of this project proposal is to complete a longitudinal clinical study of a cutaneous stimulation device in a target population of subjects with knee pathology. This work will determine the longer-term effect of the intervention on pain/function, gait/muscle function, and patient comfort.

Scientific Rationale. Knee injuries and pathologies such as anterior cruciate ligament (ACL)/meniscus tears and knee osteoarthritis (OA) are prevalent musculoskeletal conditions that cause functional limitations, pain and disability affecting patient quality of life and healthcare cost. Individuals with knee injuries who had undergone a meniscectomy or ACL reconstruction surgery and knee OA patients exhibit significant alterations in lower extremity muscle patterns involved in gait, including a weakness in the quadriceps muscle. Over the long term, an impairment in muscle activity may result in a change in mechanical stress loading of a joint and have adverse effects on the knee joint, and research increasingly suggests that such alterations may be significant predictors of onset and progression of knee OA.

Clinical guidelines for management of knee OA and associated joint injuries recommend non-pharmacological conservative interventions such as physical therapy, use of braces, elastic wraps, electrical stimulation and taping. These interventions are commonly used to improve muscle strength, joint stability and mitigate pain. However, treatment is often discontinued because of time constraints and cost involved, and hence there are limited long-term improvements.

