To address these limitations, we have developed a device which utilizes a novel design to activate deficient lower extremity muscles through the somatosensory system and cutaneous stimulation. This device exploits the cross modal plasticity of the somatosensory system that controls touch, pain and proprioception. By applying intermittent cutaneous stimulation to the thigh and shank through vibration, it may activate the mechanoreceptors in the leg and thereby induce improved muscle contraction and a functional response during walking. This study aims to assess the changes in gait patterns and pain/function resulting from the intermittent cutaneous stimulation of afferent nerves on the surface of the thigh and shank.

Focus. Using a cross-over study design, this study aims to assess the influence of the cutaneous stimulation device versus a commercially-available knee sleeve on pain, function, and knee joint mechanics.

Anticipated Impact. Knee injuries and disease cause substantial pain and disability, and their high prevalence necessitate simple interventions. Clinical guidelines for management of knee OA and associated joint injuries emphasize the importance of non-pharmacological conservative strategies. Gait modification through cutaneous stimulation may offer a low cost alternative to rehabilitation programs and current treatments to address pain, deficient muscle activation in knee OA and conditions related to development of the disease.

Methods. The objective of this study is to conduct a cross-over study to assess the influence of the cutaneous stimulation device versus a commercially-available knee sleeve. We will use a single-center, single-blind, randomized, crossover study design. Participants will be told only that we are comparing two types of treatment for their knee pain.

Interventions will include: (A) Control treatment consisting of an off-the-shelf neutral knee sleeve and (B) Active treatment consisting of the cutaneous stimulation device.

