During gait testing, each subject may be asked to walk at a variety of speeds and perform activities of daily living. A motion capture system consisting of infrared cameras and small reflective balls (markers) attached to the subjects using small double sided stickers and force platforms embedded in the floor will be used estimate subjects kinematics and kinetics during gait following the point cluster method protocol and standard inverse kinetics calculations. Pressure sensors may also be used to provide a 2 dimensional map of the pressure distribution in the stance phase of gait. EMG may be used to provide information on muscle activation. Additionally, inertial sensors may be placed on the bodies of the subjects to measure their kinematics. The markers and sensors will be placed on the bodies so that they do not impede the subject's movements in any way. Moreover, these elements do not impart excessive force. Ideally, the subject will forget that they are wearing the system. The walkway in the laboratory is well lit and free of obstacles. Outdoor testing may occur in a selected outdoor location that is also safe and unobstructed. There is little to no risk to the subjects beyond the normal risks associated with walking.

Subjects will be asked to complete questionnaires regarding pain, function, and physical activity.

Statistical Analysis Plan. Paired two-tailed t-tests will be used to assess changes in patient-reported outcomes and joint loading parameters (e.g. peak knee flexion moment) with each treatment from pre-treatment control.

Results.

- Mean +/- SD KFM at baseline for all 38 subjects : 3.14 ± 1.31
- Mean +/- SD KOOS Pain at baseline for all 38 subjects 66.25 ± 13.4
- Mean +/- SD KOOS Function at baseline for all 38 subjects 72.31 ± 15.98
- Mean +/- SD KOOS Symptoms at baseline for all 38 subjects 59.8 ± 15.58
- Mean +/- SD *change* in KFM (%Bw*Ht) separately for Treatment A and Treatment B from control (and # of subjects analyzed for each). **For slow walking**

Treatment A mean +/- SD change in KFM (%Bw*Ht) relative to control= 0.197 ± 0.374

Treatment B mean +/- SD change in KFM (%Bw*Ht) relative to control= 0.018 ± 0.725

- Statistical test used to compare the KFM and the p-values from it (separate p-values for Tx A and Tx B vs. control)
- T-test Treatment A P=0.005
- T-test Treatment B P=0.64

- Mean +/- SD *change* in KOOS Pain separately for Treatment A and Treatment B from control (and # of subjects analyzed for each).

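### The stated question is device versus sleeve, but the plan and the results contain only before/after tests within each treatment

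*Combined protocol and SAP*

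**What the plan says.** The Focus paragraph says that "this study aims to assess the influence of the cutaneous stimulation device versus a commercially-available knee sleeve on pain, function, and knee joint mechanics", and the Methods paragraph repeats that comparison as the objective. The design is stated plainly: "We will use a single-center, single-blind, randomized, crossover study design". The two treatments are "A) Control treatment consisting of an off-the-shelf neutral knee sleeve and (B) Active treatment consisting of the cutaneous stimulation device".

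Two other sentences describe an aim about the device alone. The Purpose says "This work will determine the longer-term effect of the intervention on pain/function, gait/muscle function, and patient comfort", and the rationale for the device adds that the study is to "assess the changes in gait patterns and pain/function resulting from the intermittent cutaneous stimulation".

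The Statistical Analysis Plan is one sentence. It specifies paired two-tailed t-tests of changes in patient-reported outcomes and "joint loading parameters (e.g. peak knee flexion moment) with each treatment from pre-treatment control". The Results use the same structure for knee flexion moment (KFM) and for KOOS Pain, Function and Symptoms: changes are given "separately for Treatment A and Treatment B from control (and # of subjects analyzed for each"), with "separate p-values for Tx A and Tx B vs. control". The number analysed for each treatment is called for in these headings but not printed. Only the baseline lines give a number, 38.

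**The concern.** The design can answer the comparative question, because every subject is planned to receive both treatments and can act as his or her own control. The written analysis does not use that feature. It tests each treatment against its own starting point.

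A before/after change carries more than the treatment effect. It also contains natural course, regression to the mean, expectation and the effect of repeated testing. The sleeve period is there to separate these from the effect of the device, and that separation happens only if the two changes are compared with each other.

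The documents draw no conclusion from the pattern of p-values, but a reader has nothing else to go on. For KOOS Symptoms the sleeve shows P=0.04 and the device P=0.68. It is tempting to read this as a difference between treatments. One significant and one non-significant before/after test do not make a test of the difference.

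**Working it through.** **1. What control means in the Results.** Methods calls the sleeve the control treatment, so Treatment B against control might be taken as device against sleeve. That reading fails on the text: Treatment A, which is the sleeve, is itself reported against control, and the analysis plan names the comparator as pre-treatment.

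**2. Reproducing the printed p-values.** A paired t-test on a change score is t = mean / (SD/√n) with n − 1 degrees of freedom, two-sided. The means and SDs are those in the Results. The value of n is not printed, so whole numbers up to 38 were tried. Results at n = 33 and at n = 38:

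| Outcome, treatment | Mean ± SD change | Printed p | p at n = 33 | p at n = 38 |
|---|---|---|---|---|
| KFM, A | 0.197 ± 0.374 | 0.005 | 0.0049 | 0.0025 |
| KFM, B | 0.018 ± 0.725 | 0.64 | 0.888 | 0.879 |
| Pain, A | 1.476 ± 12.286 | 0.5 | 0.495 | 0.464 |
| Pain, B | −0.391 ± 9.714 | 0.82 | 0.819 | 0.805 |
| Function, A | 4.48 ± 12.56 | 0.05 | 0.049 | 0.034 |
| Function, B | 0.64 ± 7.903 | 0.65 | 0.645 | 0.621 |
| Symptoms, A | 3.571 ± 9.47 | 0.04 | 0.038 | 0.026 |
| Symptoms, B | −0.781 ± 10.876 | 0.68 | 0.683 | 0.661 |

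At n = 33, seven of the eight agree with print within rounding. Function B is 0.6449 on the printed mean and reaches 0.6475 if the unrounded mean was 0.635. So the printed p-values behave as tests of each treatment's own change. KFM for Treatment B is the exception: its printed mean and SD do not give its printed p at any n up to 38.

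**3. What the printed figures say about sleeve minus device.** The point difference is a subtraction:

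- Pain: 1.476 − (−0.391) = 1.87
- Function: 4.48 − 0.64 = 3.84
- Symptoms: 3.571 − (−0.781) = 4.35

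Its standard error needs the within-subject correlation ρ between the two changes, which is not reported:

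SD_diff = √(s_A² + s_B² − 2ρ s_A s_B), SE = SD_diff/√n, 95% CI = difference ± t(0.975, n − 1) × SE.

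Assumptions: n = 33, the same subjects in both periods, no period adjustment, ρ from 0 to 0.7. Here t(0.975, 32) = 2.037. As an example, for Symptoms at ρ = 0, SD_diff = √(9.47² + 10.876²) = 14.42, SE = 14.42/√33 = 2.51, and the interval is 4.35 ± 2.037 × 2.51.

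| Outcome | Difference | SD_diff (ρ = 0; 0.7) | 95% CI, p at ρ = 0 | 95% CI, p at ρ = 0.7 |
|---|---|---|---|---|
| Pain | 1.87 | 15.66; 8.84 | −3.69 to 7.42, p = 0.50 | −1.27 to 5.00, p = 0.23 |
| Function | 3.84 | 14.84; 9.01 | −1.42 to 9.10, p = 0.15 | 0.64 to 7.04, p = 0.020 |
| Symptoms | 4.35 | 14.42; 7.99 | −0.76 to 9.47, p = 0.093 | 1.52 to 7.18, p = 0.004 |

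Setting p = 0.05 and solving for ρ gives about 0.52 for Function and 0.28 for Symptoms. For Pain it would take 0.91, outside the assumed range.

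**4. Does this depend on n = 33?** Over the same range of ρ:

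| n | Function p | Symptoms p |
|---|---|---|
| 32 | 0.153 to 0.022 | 0.098 to 0.004 |
| 38 | 0.119 to 0.012 | 0.071 to 0.002 |

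Both outcomes straddle 0.05 at each n. No KFM contrast is shown, because the Treatment B figures must be reconciled first.

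**The case against.** The strongest reply is that the practical consequence is small. The documents claim no benefit of the device, no printed device test is below 0.05, and every KOOS point difference favours the sleeve if a higher score is better, which the documents do not state. The Purpose also sets a device-only aim, to which a before/after change is relevant. This is fair as far as it goes. There is no false claim to withdraw. But the comparison with the sleeve is the stated Focus and objective, and even for the device-only aim an uncontrolled change is weak evidence when a control period is available.

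The illustration is also open to challenge, and here several points stand:

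- The value n = 33 is inferred. If the p-values were truncated and not rounded, n = 32 fits the same seven.
- Fewer subjects may have both changes. With 28 (assumed), the ρ thresholds rise to about 0.62 for Function and 0.40 for Symptoms.
- A negative correlation is possible. At ρ = −0.3 and n = 33, Symptoms gives p = 0.14.
- The calculation leaves out the period adjustment that the remedy asks for.

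Each of these widens the uncertainty. None supplies the missing comparison, and the omission itself rests on the text and not on any calculation.

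The KFM inconsistency for Treatment B is a separate matter. It is raised here only because it blocks a KFM contrast.

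**Conclusion.** The concern holds and should be treated as a must-fix. The objective is device versus sleeve, and neither the plan nor the Results contains that comparison for any of the four outcomes. This is certain from the wording. The printed summaries cannot settle the comparison either: for KOOS Function and Symptoms the answer at the 5% level turns on an unreported correlation, and for KOOS Pain the interval includes zero throughout the assumed range. Those ranges are an illustration and not an estimate of the trial's result.

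**What to change.** - Make the within-subject difference between device and sleeve, adjusted for period, the main analysis for each outcome. A period-adjusted paired analysis is enough. State how subjects with only one completed period are handled.
- Report the estimate, 95% confidence interval, p-value and number analysed per treatment.
- Say which visit is the pre-treatment value: study entry or the start of each period. A gait test is planned at both.
- In the Results, refer to pre-treatment baseline instead of control, so that it cannot be confused with the sleeve. Keep the before/after changes as descriptive.
- Label the new contrast as specified after the results were seen.
- Reconcile the mean, SD and p-value for KFM under Treatment B before giving a KFM contrast.

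The cost is re-analysis and the post hoc label. No new patients, visits or measurements are needed.

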Individuals with prior ACL injury/surgery, meniscus injury/surgery, and/or physician-diagnosed medial compartment knee osteoarthritis will be recruited. The participants will be 18 years or older, and both males and females will be recruited. Individuals below the age of 18 years old are excluded as they may not have reached skeletal maturity. Knee pathology subjects may be recruited through direct referrals from clinicians in primary care, rheumatology, physical medicine and rehabilitation, physical therapy, radiology, and orthopedic surgery. The group has successfully used advertising flyers to recruit subjects and we will also employ these methods for knee pathology subjects.

Subjects will be telephone screened for inclusion criteria. If the subject meets the designated criteria, he/she will be scheduled to visit the gait lab and enrolled in the study. The procedures will take approximately 2-3 hours.

At baseline testing, eligible subjects will be randomized to receive either treatment A or B for the initial 4 weeks and will receive a gait test. After the 4 weeks, the assigned treatment will be removed and a second gait test performed, and the participants will receive no treatment for 2 weeks. Following this 2-week washout period, the second randomized treatment will be

assigned for a 4-week period and a gait test performed. At the end of the 4-week period, another gait test will be performed. For each subject, the trial will last for a total of 10 weeks.

During each treatment, subjects will maintain a daily wear log, pain diary, and medication usage. Subjects will record the number of hours of brace wear each day and will be instructed to wear the brace during the active part of the day (greatest number of gait cycles).

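### The crossover is analysed without a period term: each treatment's tested change includes the effect of time, and the A-minus-B difference is clear of it only if the analysed sequences are equal in size

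*Combined protocol and SAP*

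**What the plan says.** The Methods section describes a "single-center, single-blind, randomized, crossover study design" comparing a neutral knee sleeve (A) with the cutaneous stimulation device (B). At baseline "eligible subjects will be randomized to receive either treatment A or B for the initial 4 weeks". "Following this 2-week washout period, the second randomized treatment will be" given for a further 4 weeks, and "For each subject, the trial will last for a total of 10 weeks". Gait is tested at the start and end of each treatment period. The allocation ratio, any blocking and the number in each sequence are not stated.

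The Statistical Analysis Plan is one sentence: "Paired two-tailed t-tests will be used to assess changes in patient-reported outcomes and joint loading parameters", the changes being those "with each treatment from pre-treatment control". Here the word control means the pre-treatment state, not the sleeve. No period, sequence or carry-over term is named.

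The Results section gives one mean change, SD and p-value per treatment and outcome ("separate p-values for Tx A and Tx B vs. control"), with no split by period or sequence. The baseline lines cover 38 people ("Mean +/- SD KOOS Pain at baseline for all 38 subjects 66.25 ± 13.4"). The template asks for the number analysed for each treatment, but no number is given.

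**The concern.** Randomising the order of treatments protects the comparison between them, and that protection is realised when the analysis compares A with B and allows for period. The plan does neither. Each t-test takes the change on one treatment, some of it measured in weeks 0 to 4 and some in weeks 6 to 10, and compares it with zero.

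Anything that moves scores over time regardless of treatment goes into that change. Familiarity with the gait laboratory and repeated questionnaires are plausible sources. Two separate things follow. First, the average movement over the two periods sits inside both treatments' changes and cannot be told apart from a treatment effect. Second, if more of the analysed participants took A first, A receives more of the first-period movement and B less, so the gap between them is displaced as well. At stake is whether the printed changes, some of them close to the 5% level, can be read as effects of the sleeve or the device.

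**Working it through.** **Inputs.** From Methods: two sequences (AB, BA) with periods of 4 weeks, a 2-week washout and 4 weeks. From Results: 38 at baseline, and the mean change, SD and p-value for each treatment and outcome. Not in the documents, so assumed below: the number analysed, the allocation method, the sequence sizes and the size of any period effect. The plan states no sample size, power or alpha, so there is no design figure to reproduce.

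**Step 1: do the printed results pool the periods?** Recompute each p-value with the planned test, t = mean / (SD/√n), two-sided, n-1 degrees of freedom:

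| Outcome | Printed P | n = 32 | n = 33 |
|---|---|---|---|
| KFM A | 0.005 | 0.0056 | 0.0049 |
| KFM B | 0.64 | 0.889 | 0.888 |
| Pain A | 0.5 | 0.502 | 0.495 |
| Pain B | 0.82 | 0.821 | 0.819 |
| Function A | 0.05 | 0.052 | 0.049 |
| Function B | 0.65 | 0.650 | 0.645 |
| Symptoms A | 0.04 | 0.041 | 0.038 |
| Symptoms B | 0.68 | 0.687 | 0.683 |

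Allowing for rounding or truncation, seven of the eight fit an unadjusted test on about 32 or 33 people for both treatments. KFM B fits no n up to 38, which is a separate matter. Since 32 + 32 - 38 = 26, at least 26 people contributed to both treatments. With the order randomised, each treatment's mean therefore mixes first-period and second-period recipients.

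**Step 2: where the period effect goes.** Let p be the analysed fraction in sequence AB, π1 and π2 the mean changes in periods 1 and 2 unrelated to treatment, d = π1 - π2, and τ the treatment effects.

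- E[change on A] = τA + pπ1 + (1-p)π2 = τA + (π1+π2)/2 + (p-1/2)d
- E[change on B] = τB + (1-p)π1 + pπ2 = τB + (π1+π2)/2 - (p-1/2)d
- E[A-B] = τA - τB + (2p-1)d

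The term (π1+π2)/2 stays in both changes for every p. Equal sequences remove only the d term. Simulation with no treatment effect and SD 10 agrees: at 16:16 with π1 = 3 and π2 = 0, the mean changes are +1.50 for A, +1.49 for B and 0.00 for A-B. Each within-treatment test then rejects about 13% of the time at a nominal 5%, while the A-B test rejects about 5%. At 20:12 with π1 = +3 and π2 = -3, A-B averages +1.47, against 0.25 × 6 = 1.5 from the formula.

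**Step 3: how unequal might the sequences be?** Assume 32 analysed and unrestricted 1:1 allocation.

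- Expected |2p-1| = 0.14, so the typical shift is 0.14d in A-B and 0.07d in each treatment's change.
- A 20:12 split or worse, in either direction, has probability 0.215. At 20:12, p - 1/2 = 0.125 and 2p - 1 = 0.25.
- If instead 19 were allocated to each sequence and 6 were not analysed, the worst case is 19:13, with factors 0.094 and 0.188.

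| Assumed d (KOOS points) | Each change at 20:12 | A-B at 20:12 | A-B at expected imbalance |
|---|---|---|---|
| 2 | 0.25 | 0.50 | 0.28 |
| 5 | 0.63 | 1.25 | 0.70 |
| 8 | 1.00 | 2.00 | 1.12 |

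For scale, the printed A-B gaps are 1.476 + 0.391 = 1.87 (Pain), 4.48 - 0.64 = 3.84 (Function) and 3.571 + 0.781 = 4.35 (Symptoms).

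**Step 4: sensitivity of a printed result.** For Symptoms A at n = 32, the SE is 9.47/√32 = 1.674 and the two-sided 5% threshold is 3.414. The printed 3.571 exceeds it by 0.16. Holding the SD fixed, that margin is used up by d of about 0.16/0.094 = 1.7 points at 19:13, or about 1.25 at 20:12. An average period change (π1+π2)/2 of 0.16 points would do the same at any split.

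**Step 5: lost precision.** With equal sequences, an unmodelled period difference adds d²/4 to the variance of each treatment's change. At d = 5 this is 6.25, or 6.25/12.286² = 4% for Pain A and 6.25/9.714² = 7% for Pain B.

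**The case against.** The strongest reply is that randomisation already deals with the period effect in A-B. Under unrestricted allocation the expectation of 2p-1 is zero, so a simple paired A-B contrast is unbiased over randomisation, and its SD already includes the period variation. This stands. In simulation (32 analysed, SD of A-B assumed to be 14, no treatment effect), the type I error of that contrast stays near 5% for d of 2, 5 or 8. It rises only within the 20:12-or-worse splits, to roughly 7 to 8% at d = 5 and 10 to 11% at d = 8. A reader might infer that omitting the period term systematically biases the comparison. The documents do not support that unless dropout differed by sequence, which is not shown.

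The reply does not rescue the tests the plan actually specifies. Those are within-treatment changes, and the average period change remains in them at any split. A reader might also infer that equal sequences would clear the printed t-tests; by Step 2 they would not.

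Other limits also stand. Pooling is inferred from the p-values, not stated. The plan does not say whether the pre-treatment value is the start of each period or one common baseline; the point holds under either reading, with π2 defined accordingly. Silence on blocking does not show that there was none. It is tempting to suppose that first-period improvement must be large because people entered by referral or with symptoms at their worst. Methods says only that referral is one possible route, alongside flyers, and entry rests on injury, surgery or diagnosis, with no symptom threshold given. The lost precision is small.

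**Conclusion.** The omission is real and worth correcting, at moderate weight. The within-treatment changes cannot be separated from time, whatever the sequence sizes. The A-minus-B difference is free of the period effect only if the analysed sequences are equal; otherwise it is displaced by (2p-1)d.

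The actual displacement cannot be quantified, because neither the sequence sizes nor any results by period are reported; it may be zero. The sizes above rest on assumed values: 32 analysed (well supported by the p-values), unrestricted allocation, and d of 2 to 8 KOOS points. A reader might conclude that the Symptoms result for A is an artefact of period. The documents show only that its margin over the 5% threshold is thin enough for a modest period effect to matter, not that such an effect occurred. Confidence is medium for that reason.

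**What to change.** For each outcome, replace the two separate t-tests with a linear mixed model on the per-period change, with fixed effects for treatment, period and sequence and a random subject effect.

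- Report the period-adjusted A-minus-B difference with its confidence interval as the treatment-effect result. This also answers the stated aim of comparing the device with the sleeve.
- Tabulate n and mean change by sequence and period, so that a reader can see whether the sequences were balanced and whether d was appreciable.
- State which measurement is the pre-treatment value for each period.
- Present the within-treatment changes as descriptive. Adding a period term, or averaging equally over periods, still leaves (π1+π2)/2 in them.

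The cost is revised SAP wording, one model per outcome and one or two residual degrees of freedom. It needs each participant's allocated order and per-period values, which the design already generates. If the sequences prove balanced or d negligible, the table will show it and the A-minus-B estimate will barely move.

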Treatment A mean +/- SD change in KOOS Pain relative to control= 1.476 ± 12.286

Treatment B mean +/- SD change in KOOS Pain relative to control= -0.391 ± 9.714

- Statistical test used to compare KOOS Pain and the p-values from it (separate p-values for Tx A and Tx B vs. control)
- T-test Treatment A P=0.5
- T-test Treatment B P=0.82

- Mean +/- SD *change* in KOOS Function separately for Treatment A and Treatment B from control (and # of subjects analyzed for each).
 - Statistical test used to compare KOOS Function and the p-values from it (separate p-values for Tx A and Tx B vs. control)

Treatment A mean +/- SD change in KOOS Function relative to control= 4.48 ± 12.56

Treatment B mean +/- SD change in KOOS Function relative to control= 0.64 ± 7.903

- T-test Treatment A P=0.05
- T-test Treatment B P=0.65

- Mean +/- SD *change* in KOOS Symptoms separately for Treatment A and Treatment B from control (and # of subjects analyzed for each).
- Treatment A mean +/- SD change in KOOS Symptoms relative to control= 3.571 ± 9.47
- Treatment B mean +/- SD change in KOOS Symptoms relative to control= -0.781 ± 10.876

- Statistical test used to compare KOOS Symptoms and the p-values from it (separate p-values for Tx A and Tx B vs. control)
- T-test Treatment A P=0.04
- T-test Treatment B P=0.68

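### The Treatment B change in KFM (0.018 ± 0.725) and its P=0.64 cannot both come from the planned paired two-tailed t-test on 38 or fewer subjects

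*Combined protocol and SAP*

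**What the plan says.** The Statistical Analysis Plan section of the combined document sets the method: "Paired two-tailed t-tests will be used to assess changes in patient-reported outcomes and joint loading parameters", in each case for the change from the pre-treatment control condition under each treatment.

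The Results section gives the baseline sample as "Mean +/- SD KFM at baseline for all 38 subjects : 3.14 ± 1.31". For the active device in slow walking it then prints "Treatment B mean +/- SD change in KFM (%Bw*Ht) relative to control= 0.018 ± 0.725" and, under the test results, "T-test Treatment B P=0.64". The corresponding test result for the knee sleeve is "T-test Treatment A P=0.005".

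The heading over the KFM changes asks for the mean, the SD and the number analysed for each treatment, but no number follows. The Methods section says of gait testing that "each subject may be asked to walk at a variety of speeds", so KFM data may exist for more than one speed.

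**The concern.** A paired t-test has no free parameter once the mean change, the SD of the change and the number of pairs are given. A mean of 0.018 against an SD of 0.725 is a standardised change of 0.018/0.725 = 0.025. With a few dozen subjects that should give a P close to 0.9, not 0.64.

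This is the only joint-mechanics result reported for the active device, and knee joint mechanics is one of the things the study set out to compare. If a figure is wrong, a reader who uses the row for an effect size, a precision estimate, a sample-size calculation or a meta-analysis does not know which figure to trust.

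**Working it through.** **Inputs.** From the Statistical Analysis Plan: paired, two-tailed t-test. From Results: mean 0.018, SD 0.725, P=0.64, and 38 subjects at baseline. The analysed n is not printed, so every n from 2 to 38 was tried, taking one pair per subject.

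**Step 1: reproduce the printed P.** t = mean / (SD/√n), with n − 1 degrees of freedom.

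| n | t | two-tailed P |
|---|---|---|
| 20 | 0.111 | 0.913 |
| 32 | 0.018/(0.725/√32) = 0.140 | 0.889 |
| 33 | 0.018/(0.725/√33) = 0.143 | 0.887 |
| 38 | 0.018/(0.725/√38) = 0.153 | 0.879 |

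P falls as n rises, from 0.978 at n=2 to 0.879 at n=38. With the rounding that most favours a small P (mean 0.0185, SD 0.7245), n=38 gives 0.876. The printed 0.64 is not reproduced at any admissible n.

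**Step 2: the n that would be needed.** Allowing for rounding of the mean and SD, P=0.64 requires 327 to 387 pairs if P was rounded to two decimals, or 317 to 376 if it was truncated. Dividing by 38, that is roughly 8 to 10 pairs per subject.

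**Step 3: other readings of the row.**

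| Reading | P |
|---|---|
| One-tailed, n=32 / 33 / 38 | 0.445 / 0.444 / 0.440 |
| One-tailed, opposite direction | 0.555 / 0.556 / 0.560 |
| Normal approximation, n=38 | 0.878 |
| Two knees per subject, 76 pairs | 0.829 |
| 0.725 taken as a standard error, n=32 | 0.98 |
| Unpaired, using the baseline SD of 1.31 | 0.95 |

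None gives 0.64.

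**Step 4: does the formula fit the other rows?** The third and fourth columns use the mean and SD as printed. The last column gives the n compatible with the printed P once rounding of the mean and SD is allowed.

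| Row | Printed P | P at n=32 | P at n=33 | n if P rounded / truncated |
|---|---|---|---|---|
| KFM A | 0.005 | 0.0056 | 0.0049 | 32–33 / 32–33 |
| **KFM B** | **0.64** | **0.889** | **0.887** | **327–387 / 317–376** |
| KOOS Pain A | 0.5 | 0.502 | 0.495 | 26–40 / 20–32 |
| KOOS Pain B | 0.82 | 0.821 | 0.819 | 31–34 / 29–32 |
| KOOS Function A | 0.05 | 0.052 | 0.049 | 32–34 / 31–32 |
| KOOS Function B | 0.65 | 0.650 | 0.645 | 31–33 / 30–32 |
| KOOS Symptoms A | 0.04 | 0.041 | 0.038 | 31–34 / 30–32 |
| KOOS Symptoms B | 0.68 | 0.687 | 0.683 | 33–34 / 32–33 |

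Seven rows share n=33 if the P values were rounded and n=32 if they were truncated. For example, "Treatment B mean +/- SD change in KOOS Symptoms relative to control= -0.781 ± 10.876" agrees with its P of 0.68. Only the Treatment B KFM row fails.

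**Step 5: what each possible correction implies.** P=0.64 corresponds to t = 0.4723 / 0.4722 / 0.4716 at n = 32 / 33 / 38. The 95% CI half-width is t(0.975, n−1) × SD/√n, with t(0.975) = 2.040 / 2.037 / 2.026.

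- Mean and SD right: P is 0.889 / 0.887 / 0.879, with CI −0.243 to 0.279 / −0.239 to 0.275 / −0.220 to 0.256.
- Mean and P right: SD = 0.018 × √n / t = 0.216 / 0.219 / 0.235, with CI about −0.06 to 0.10 at each n.
- SD and P right: |mean| = 0.725 × t / √n = 0.061 / 0.060 / 0.055. If the sign is positive as printed, the half-widths of 0.261 / 0.257 / 0.238 give CIs of about −0.20 to 0.32 / −0.20 to 0.32 / −0.18 to 0.29.

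**The case against.** The best argument on the other side is about weight. Both 0.64 and about 0.88 are far from significance, the document reports only within-treatment tests, and no conclusion in it is shown to rest on this P. If P alone is wrong, the estimate and its interval stand. That is fair as far as it goes, and it is why the point calls for a correction and does not overturn a finding. It does not cover the case where the mean or the SD is the wrong entry, which changes the estimate or its precision about threefold.

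A second argument is that the calculation equates pairs with subjects, while several knees or walking trials per subject could have been analysed. Two knees per subject still gives 0.829. Pooling 8 to 10 trials per subject could reach 0.64, but nothing in the document describes it, and the Treatment A KFM row fits only 32 to 33 pairs.

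Third, the results line says only that a t-test was used, so a different test for this row is not strictly excluded. The plan names one test, however, and the other seven rows follow it. The text was also extracted from a PDF, but the line shows no sign of damage.

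Finally, there are weak clues to the cause. The value 0.64 is also the Treatment B mean change in KOOS Function, which would fit a copying slip in P. The Treatment B KFM SD is 0.725/0.374 = 1.94 times that of Treatment A, whereas the same ratio for KOOS Pain, Function and Symptoms is 0.79, 0.63 and 1.15, so the SD is also suspect. These clues point in different directions and settle nothing.

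**Conclusion.** The concern holds. Under the planned test, the printed mean, SD and P are mutually incompatible for any n up to 38: the smallest attainable P is 0.876, against 0.64 as printed. This does not depend on the missing analysed n. It does assume one pair per subject and that the row was tested as the plan says; the fit of the other seven rows supports both. The sizes of the possible corrections do depend on n, and the values of 32 and 33 are inferred from those rows, not stated.

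At least one figure is wrong, or comes from another walking speed or analysis set. The statement that the Treatment B change is not significant is unaffected. What is unsettled is the size of the change and its precision. The correction should be made, and confidence in the inconsistency is high.

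**What to change.** Recompute the Treatment B slow-walking KFM mean change, SD, number analysed and P from the subject-level data. Confirm that all four come from the same walking speed and the same analysis set, and correct whichever figure is wrong. Print the n beside the result, as the heading already requires, and preferably the 95% confidence interval. If the unit of analysis was anything other than one pair per subject, or a different test was used, say so in the same line.

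The cost is one re-run on existing data and one corrected results line.
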